8.4 Recurrent Tumor Pain/New Tumor Pain

Additional targeted therapies (cryoablation, RFA, MWA, HIFU, radiation, surgery, etc.) are not permitted on an index tumor per this protocol. If the investigator feels additional targeted therapy is appropriate, the subject will be discontinued from the study.

If a new painful tumor is identified during the follow-up period, targeted therapies (cryoablation, RFA, MWA, HIFU, radiation, surgery, etc.) are permitted, provided that the region of identifiable pain may be clearly distinguished from the region/tumor treated during the initial cryoablation procedure.

Other therapies, including pain medications and chemotherapy are permitted.

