A sample size of 42 achieves 80% power to detect superiority using a one-sided t-test when the margin of superiority is -2.0 and the true difference between the mean and the reference value is -3.2. The data are drawn from a single population with a standard deviation of 2.7. The significance level (alpha) of the test is 0.025.

Galil Medical completed a pilot study for the same indication. In this pilot study, 28 subjects were enrolled and approximately 82% (23/28) of subjects completed the 7 week follow up interval. Nearly all of the attrition (10/11 early withdrawals) observed in the pilot study was attributed to death due to disease progression. This is similar to the population accrued for the Callstrom et al study with the same duration of follow up 57% (35/61) completed 7 weeks. In the Goetz et al (RFA) multicenter study, 77% (33/43) completed the study at 24 weeks. The comparative analysis of study participation summarized the attrition for each of these studies in which ablation was used to treat metastatic bone lesions. The significant attrition between 7 and 12 weeks follow up should be noted across all studies and is not unanticipated due to this population with metastatic disease. Furthermore, the 30% attrition rate at 8 weeks for this

terminally ill population was acknowledged by FDA reviewers in preparation for the launch of this study.

The final study sample size accounts for 30% attrition to ensure the appropriate number of evaluable subjects at 8 weeks. Additionally, sensitivity analyses will be conducted using methods attempt to account for drop-out subjects. Missing at random (MAR) approach is assumed as the pilot data shows nearly all attrition will be due to subject death from disease progression unrelated to cryoablation treatment. We do not anticipate any systematic differences between those who do and do not drop out.

With an attrition rate at 8-weeks estimated to be 30%, the total treated study sample size will be 60 subjects. This sample size will be considered clinically sufficient to give indications of device effectiveness.

General Analysis Methods

Data will be analyzed using descriptive statistics. Continuous variables (e.g., age) will be summarized by the number of patients, mean, standard deviation, median, interquartile range, minimum and maximum. Categorical variables (e.g., race) will be summarized by frequencies and percentages of patients in each category.

Analysis Populations

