Intent-to-Treat (ITT) analyses will be performed on all subjects with a Galil Medical cryoablation system as the attempted treatment. Endpoints will also be evaluated using per protocol population (PP).

Efficacy Endpoint Analysis

Primary Efficacy Endpoint

The primary endpoint for this study will be measured as follows: improvement in self-reported pain scores defined by ≥ 2 point reduction in worst pain in the last 24 hours using the Brief Pain Inventory (BPI) from baseline to 8 weeks. A mean difference of 2 points reduction is considered clinically significant.

Analysis Methods

Pain assessments using the BPI will be made by examining the average difference of pre- and post-treatment worst pain in 24 hours at week 8 follow-up as measured on the Brief Pain Inventory (BPI) scale. A mean pain reduction of 2 points from baseline in worst pain score is considered clinically meaningful.

Calculations:

- 8-Week follow-up minus baseline worst pain will be calculated for each subject.
- Mean change over all subjects will be calculated.

- The mean reduction in pain at 8-weeks will be evaluated for clinical meaning.

To be considered clinically meaningful the 95% confidence interval's upper bound on the mean reduction in worst pain score must be less than -2.

Subjects without missing endpoint data will be considered completers. Intent-to-Treat Completers (ITTC) analysis as well as Per-Protocol Completers (PPC) analysis will be supplemented by missing data sensitivity analyses. Sensitivity analyses will be performed on the primary efficacy endpoint using two methods of missing data imputation: multiple imputation and last observation carry forward. These imputation methods will be employed on both the ITT and PP populations resulting two additional outcome analyses: Intent-to-Treat Imputed (ITI) and Per-Protocol Imputed (PPI). Of the four analyses, the primary hypothesis test will be considered the ITI analysis with multiple imputation.

For any complete case analysis, the subjects missing BPI at week 8 would be excluded from the analysis. For any imputed analysis, the subjects missing BPI at week 8 would use the imputed week 8 value to determine if the responder threshold was met for that subject.

The multiple imputation model will consider the BPI score at each time point (BPI at 1, 4, 12, 16, 20, and 24 weeks will be part of analyses) in addition to age and gender.

Safety Endpoint Analysis

Safety Endpoint

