The safety endpoint for this study is to assess the incidence and severity of intraoperative events, post-operative adverse events, serious adverse events and unanticipated adverse device effects.

Analysis Methods

Point estimates and two-sided Exact 95% confidence intervals will be generated for procedural related events in the following categories:

- intra-operative events
- post-operative adverse events
- serious adverse events
- unanticipated adverse device effects

The safety analysis will be performed on the per-protocol population. No formal statistical hypothesis testing will be performed for safety endpoints.

Other Endpoint Analyses

Other Endpoints

Other endpoints for this study will include, but are not limited to:

- A responder analysis will be conducted. A responder is defined as a subject having ≥ 2 point reduction in the worst pain score in the last 24 hours using the BPI and no more than 25% increase in medication use (morphine equivalent) from baseline to 8 weeks
- Quality of Life (QoL) as measured by the overall BPI pain interference average score from baseline to 1, 4, 8, 12, 16, 20, and 24 weeks after cryoablation
- Change in physical function as measured by Karnofsky Performance Status (KPS) from baseline to 1, 4, 8, 12, 16, 20, and 24 weeks after cryoablation
- Additional therapies for persistent/recurrent pain associated with the index tumor under study or new metastases through 24 weeks
- Change in analgesic medications (morphine equivalent daily dosing and NSAID use) from baseline to 1, 4, 8, 12, 16, 20, and 24 weeks after cryoablation
- Difference in worst pain scores from baseline to 1, 4, 12, 16, 20, and 24 weeks after cryoablation as measured on the numeric 0 to 10 BPI scale
- Difference in average pain scores from baseline to 1, 4, 8, 12, 16, 20, and 24 weeks after cryoablation as measured on the BPI numeric rating scale
- Self-assessed Overall Treatment Effect (OTE) at 1, 4, 8, 12, 16, 20, and 24 weeks after cryoablation

Tumor Characteristics

Tumor characteristics will include, but are not limited to:

- Histology of primary cancer
- Proof of metastases
- Location of the index tumor
- Size of the index tumor

Physical Function

Physical function is considered routine clinical practice in medicine. Specifically, in oncology practice, physical function assessments such as the Karnofsky scale have been incorporated. This study will use the Karnofsky scale to assess physical function.

Additional Data Summaries

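### The SAP's missing-data rules for the responder analysis refer only to BPI: morphine-equivalent dose has no rule, and index-tumor retreatment or death before week 8 has no responder status

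*SAP*

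**What the plan says.** The responder analysis is listed among the other endpoints (Protocol 5.3; SAP, Other Endpoints). A responder must have a reduction of 2 points or more in BPI worst pain and "no more than 25% increase in medication use (morphine equivalent) from baseline to 8 weeks".

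Missing data are handled in the SAP's Analysis Methods for the primary efficacy endpoint, which is pain alone. There are two rules:

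- Complete case: "For any complete case analysis, the subjects missing BPI at week 8 would be excluded from the analysis".
- Imputed: a subject without week-8 BPI takes the imputed week-8 value, and that value decides whether the responder threshold was met. On the model, the SAP says: "The multiple imputation model will consider the BPI score at each time point". Age and gender are the only other variables named.

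Protocol 8.4 does not permit further targeted therapy on the index tumor: "If the investigator feels additional targeted therapy is appropriate, the subject will be discontinued from the study". Neither document gives a responder status to that event or to death.

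On dose, Protocol 6.7 asks for the last known 24-hour opioid or NSAID intake after death or loss to follow-up, if it is known. Appendix E takes the last complete 24 hours of life as the final morphine-equivalent dose. The SAP does not connect either provision to the responder analysis.

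**The concern.** The endpoint has two components, and the missing-data rules cover one. Three gaps follow.

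- If the threshold sentence refers to the composite, subjects with observed data must pass both conditions while subjects with imputed data are judged on pain alone.
- If it refers to pain alone, no imputation is specified for the composite, and only the complete-case rule is left.
- Both rules are triggered by missing week-8 BPI. A subject with week-8 pain but no week-8 dose has no rule on either reading.

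The complete-case rule also removes subjects whose absence may itself be an outcome. Someone discontinued under 8.4 because the index tumor needed more treatment leaves the denominator if week-8 BPI is missing, although the need for retreatment suggests that palliation did not last. The SAP's missing-at-random argument rests on deaths from disease progression and does not mention retreatment.

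Pain medication is freely permitted during follow-up, and this is the only listed endpoint that combines pain relief with analgesic use. With the rules unsettled, materially different rates could each be called the responder rate after the data are seen.

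**Working it through.** **The plan's own figures.** The SAP states "A sample size of 42 achieves 80% power to detect superiority using a one-sided t-test", with "margin of superiority is -2.0 and the true difference between the mean and the reference value is -3.2". It adds: "The data are drawn from a single population with a standard deviation of 2.7" and "The significance level (alpha) of the test is 0.025". The effect beyond the margin is 3.2 − 2.0 = 1.2. The noncentral t distribution gives power of 79.3% at n = 41 and 80.3% at n = 42, so 42 reproduces. Attrition: 42 / (1 − 0.30) = 60, so the plan expects 18 of 60 without week-8 data. The documents state no responder rate, so what follows is an illustration.

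**Inputs**
- Mean change −3.2, SD 2.7 (SAP, Sample Size Justification).
- Missing share m = 30% (planning value). The week-7 figures that the SAP cites give 5/28 = 17.9% (sponsor's pilot) and 26/61 = 42.6% (multicenter cryoablation study).
- q = share of pain responders whose dose rises by more than 25%. The documents give no figure; **assumed** 5% to 30%, and the same in missing subjects.

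**Formulas**
- Pain component, taking change as normal: P = Φ((3.2 − 2.0)/2.7) = Φ(0.444) = 0.672.
- Both components: C = P(1 − q). This is the completer rate. It is also the full-sample rate if missing subjects respond like completers.
- Missing scored on pain alone: (1 − m)C + mP. The excess over C is m·q·P.
- All missing counted as failures: (1 − m)C.

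| m | q | Complete case | Missing scored on pain alone | All missing as failures |
|---|---|---|---|---|
| 30% | 5% | 63.8% | 64.8% | 44.7% |
| 30% | 10% | 60.4% | 62.5% | 42.3% |
| 30% | 30% | 47.0% | 53.1% | 32.9% |
| 17.9% | 10% | 60.4% | 61.6% | 49.7% |
| 42.6% | 10% | 60.4% | 63.3% | 34.7% |

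**Omitting dose.** At m = 30% the excess is 0.30 × 0.05 × 0.672 = 1.0 point, up to 0.30 × 0.30 × 0.672 = 6.0 points. Over m from 17.9% to 42.6% and q from 5% to 30% it is 0.6 to 8.6 points.

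**Denominator.** At m = 30%, q = 10%, the gap is 60.4 − 42.3 = 18.1 points (8.4 to 27.2 over the full range). If only half of the missing are deaths or retreated failures and the rest respond like completers, the full-sample rate is 0.604 × (1 − 0.15) = 51.4%, and the completer rate exceeds it by 9.1 points.

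**Sensitivity to whole-number scores.** With a continuity correction P = Φ((3.2 − 1.5)/2.7) = 0.736. At q = 10%, m = 30%, the completer rate is 0.736 × 0.9 = 66.2% against 0.7 × 66.2 = 46.3%, a gap of 19.9 points. The conclusion does not depend on this choice.

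**The case against.** The strongest reply is that the SAP may never score the composite on imputed pain. The threshold sentence stands under the primary endpoint, which has its own 2-point pain threshold and no dose condition, and imputation is specified only for that endpoint. A reader might infer that the SAP definitely scores about 30% of subjects on half of the definition. The text does not establish that. It is one of two readings, and 30% is a planning value. The other reading still leaves the composite with no imputation rule.

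Second, dose is not wholly neglected. Besides Protocol 6.7 and Appendix E, section 8.6 asks early terminators to return for final assessments, and the SAP includes available dropout data where possible. This stands, but it does not close the gap. The last-known dose is collected only if known, and neither 6.7 nor Appendix E names subjects discontinued for retreatment. The SAP also does not say whether an earlier dose may be paired with an imputed week-8 pain score.

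Third, a reader might infer that both versions necessarily overstate the rate. For pain-only scoring the direction is certain, given the same imputed pain values. For the complete-case rate it is conditional. The SAP assumes data missing at random and expects no systematic difference between those who drop out and those who do not. On that footing the completer rate is not biased, and counting missing subjects as failures is a choice of estimand.

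Fourth, a reader might set the result beside the focused-ultrasound trial in Protocol 1.3. Neither document plans this, and that trial used no dose increase at 3 months, against a 25% allowance at 8 weeks here. A different denominator would not make the two comparable.

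**Conclusion.** The concern holds as a gap in the responder rules. On one reading the composite is scored without dose for subjects with imputed pain, which equals or raises the rate: about 1 to 6 points at 30% missing, on an assumed dose-failure share of 5% to 30%. On the other reading only the complete-case rule applies, and retreated subjects and deaths without week-8 BPI leave the denominator. That overstates the rate if those events count as non-response, or if dropouts respond less often.

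The denominator matters more than the dose omission: about 60% against 42% in the illustration. That contrast rests on a normal distribution with the plan's mean and SD, 30% missing, 10% dose failure, and all missing counted as failures. It is an upper bound on the effect of death and retreatment, because some subjects will be missing for other reasons.

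The consequence is limited. This is an other endpoint without a hypothesis test or success criterion, and the primary test is on mean change in worst pain.

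**What to change.** Amend the SAP's wording on the responder analysis:

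1. State whether the imputed threshold is pain alone or the composite.
2. Classify a subject discontinued for index-tumor treatment before week 8 as a non-responder in every responder analysis, so that the subject stays in the denominator.
3. In the imputed analysis, impute week-8 morphine-equivalent dose jointly with week-8 pain and apply both conditions. Say whether the last-known dose from Protocol 6.7 and Appendix E is used, and for whom.
4. Beside the completer rate, report a rate with all ITT subjects in the denominator, counting deaths and any other missing week-8 component as non-response.

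Which rate leads the report is a matter of preference; both should be shown. The cost is SAP text, a dose term in the imputation model and one extra table, using data already planned for collection. The downside is that a lower rate will appear beside the completer rate, and the all-ITT version counts a merely missed visit as failure.

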8 STUDY PROCEDURES

The study schedule of events and the specific procedures performed at each visit are shown in Table 1, Schedule of Events. Each subject will undergo a total of 9 visits, including a screening visit, the procedure visit, 7 post-operative visits. In the event the subject is not able to return for office follow up visits, the follow up assessment may be conducted via telephone. More visits may be required if medically necessary.

The remainder of this page is intentionally blank

Table 1: Schedule of Study Events

Procedures	Screening	Baseline Assessment ^b (within 24 hrs of cryo)	Procedure ^a	W 1 ^d ±5 days	W 4 ^d ± 12 days	W 8 ^d ± 12 days	W 12 ^d ± 12 days	W 16 ^d ± 12 days	W 20 ^d ± 12 days	W 24 ^{d,e} ± 12 days
Informed Consent	X									
Inclusion/Exclusion	X									
Medical Comorbidities	X									
Targeted Medical History	X									
Demographics	X									
Pain Medication Assessment	X ^c	X		X	X	X	X	X	X	X
KPS	X ^c	X		X	X	X	X	X	X	X
BPI-SF Question #3	X ^c									
BPI-SF		X		X	X	X	X	X	X	X
Tumor characteristics			X							
Cryoablation Procedure			X							
Safety Assessments			X	X	X	X	X	X	X	X

^a The procedure is recommended to be performed within 14 days of the screening visit.

^b The Baseline Assessment should be completed within 24 hours prior to the cryoablation procedure. Evaluation of the inclusion/exclusion criteria should be re-evaluated prior to the cryoablation procedure to ensure criteria are met.

^c In the event the screening visit is completed within 24 hours of the cryoablation procedure, a separate BPI-SF #3 is not required. Complete the BPI-SF, KPS, and Pain Medication Assessment per the Baseline Assessment requirement.

^d In the event a subject is unable to return for a scheduled office visit follow up, the visit may be conducted via telephone.

^e Week 24/Study Completion or Early Termination

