8.2 Baseline

The following items will be completed within 24 hours prior to the cryoablation procedure and will serve as baseline information for all applicable protocol directed evaluations.

- BPI Questionnaire
- KPS
- Documentation of pain medication (opioid and/or NSAID) and reason for use

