9.5 Physical Performance

Physical function assessments will be measured using the standardized scale from the Karnofsky Performance Status (KPS). The KPS is a standard way of measuring the ability of cancer patients to perform ordinary tasks. The scores range from 0 to 100. A higher score means the patient is better able to carry out daily activities. KPS may be used to determine a patient's prognosis, to measure changes in a patient's ability to function. (See Appendix D)

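### The imputation model behind the primary test leaves out KPS and does not name baseline worst pain; the mean change is biased if either drives dropout and predicts week-8 pain beyond the modelled variables

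*SAP*

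**What the plan says.** The imputation model is defined in one place, the SAP's Analysis Methods under Primary Efficacy Endpoint: "The multiple imputation model will consider the BPI score at each time point", followed in brackets by "BPI at 1, 4, 12, 16, 20, and 24 weeks will be part of analyses) in addition to age and gender". The SAP's Handling of Missing Data section and Protocol 11.3 and 11.4.2 repeat the imputation plan without naming a variable. The endpoint is a change score: "8-Week follow-up minus baseline worst pain will be calculated for each subject". In the imputed analyses "the subjects missing BPI at week 8 would use the imputed week 8 value". The intent-to-treat imputed analysis with multiple imputation is the designated primary test, and success requires the upper 95% confidence bound to fall below -2.

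Both variables in question are collected. Protocol Table 1, footnote b: "The Baseline Assessment should be completed within 24 hours prior to the cryoablation procedure". Section 8.2 lists the BPI and KPS in that assessment and says they "will serve as baseline information for all applicable protocol directed evaluations". Table 1 schedules KPS alongside the BPI at every follow-up visit. On the meaning of KPS, Protocol 9.5 says: "KPS may be used to determine a patient's prognosis, to measure changes in a patient's ability to function".

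**The concern.** Multiple imputation gives a valid answer only if data are missing at random given the variables in the model. The SAP's Sample Size Justification assumes missing at random because pilot attrition was nearly all death from progression. Yet the model contains no measure of function or disease status. Subjects who die or leave before week 8 have no week 12 to 24 scores, so most of the listed BPI variables cannot help them. On the literal list, a subject lost before week 1 is imputed from age and gender alone, although pain and KPS were recorded the day before treatment.

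Baseline is a matter of reading. It is a scheduled BPI assessment, so the general phrase may cover it. The bracketed list cannot be complete, since it also leaves out week 8. But two programmers could build different models for the primary test.

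Bias needs two conditions: the variable is related to dropout, and it predicts week-8 pain beyond the BPI scores, age and gender already in the model and observed for that subject. Its direction depends on who drops out.

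**Working it through.** **The plan's own figures.** Distance from the margin 3.2 - 2.0 = 1.2; SD 2.7; one-sided alpha 0.025; n = 42. The noncentrality is 1.2/2.7 × √42 = 2.88, which gives 80.3% power (79.3% at n = 41). Treated subjects: 42/0.70 = 60. Imputed: 60 - 42 = 18. All reproduce.

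**Inputs not in the documents (assumed).** Baseline SD 1.7; baseline to follow-up correlation 0.2 to 0.5; correlations among follow-up scores 0.5 to 0.6; KPS-pain correlation -0.15 to -0.3; KPS-baseline correlation -0.2; dropout log-odds 0.5 to 1 per SD. Dropout is monotone, one third each before week 1, in weeks 1-4 and in weeks 4-8.

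**Formula.** For an omitted variable Z,

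bias in mean change ≈ -(fraction missing) × (coefficient of Z on week-8 pain given the modelled, observed variables) × (mean Z in dropouts minus mean Z in completers).

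**By hand, mid-range** (correlation 0.35, KPS-pain -0.2, log-odds 0.7). The week-8 SD s solves 2.7² = 1.7² + s² - 2(0.35)(1.7)s, so s = 2.775.

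- *KPS omitted, baseline in.* Given baseline, the KPS coefficient is 2.775 × (-0.2 + 0.35 × 0.2)/(1 - 0.2²) = -0.376 point per SD. Adding week 1, then week 4 (follow-up correlations 0.5, 0.55, 0.6), it is -0.219, then -0.133; the average is -0.243. A log-odds of 0.7 at 30% dropout puts dropouts about 0.64 SD lower on KPS. Bias ≈ -0.30 × 0.243 × 0.64 = -0.05.
- *Literal list, higher-pain dropout.* For dropouts before week 1, week-8 pain is imputed too low by 0.35 × 2.775 × 0.64 = 0.62. For the later two intervals the shortfall is about 0.32 and 0.18. Bias ≈ -0.30 × (0.62 + 0.32 + 0.18)/3 = -0.11.

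**Simulation of the full procedure.** 10,000 trials per setting, n = 60, 20 imputations, Rubin's rules with small-sample degrees of freedom, age and gender in every model as unrelated covariates. Monte Carlo error is about 0.003 point for bias and 0.2 percentage points for false success, which is the success rate at a true change of -2.0.

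| Model | Dropout | Bias, points | False success |
|---|---|---|---|
| KPS omitted, baseline in | lower KPS, weak | -0.016 to -0.024 | 2.2-2.4% |
| same | mid-range | -0.037 to -0.043 | 2.6-2.7% |
| same | strong | -0.091 to -0.108 | 3.5-3.9% |
| same, KPS unrelated to pain | lower KPS, strong | -0.001 | 2.3% |
| Literal list | higher pain, weak | -0.039 | 2.4% |
| same | mid-range | -0.105 | 3.2% |
| same | strong | -0.219 | 4.9% |
| Baseline and KPS both in | any of these | at most 0.01 in size | 1.7-2.2% |

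If lower-pain subjects drop out under the literal list, the bias reverses and false success falls to about 1% at mid-range (0.4% at the extreme). The intervals are slightly wide (mean standard error 1.01 to 1.08 times the true SD of the estimate), so an unbiased model sits below 2.5%.

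**Dropout unrelated to both.** There is no bias on any reading. Leaving baseline out raises the imputed SD of change to 2.81-2.96, against 2.77-2.80 with baseline in (true value 2.7).

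| Baseline to follow-up correlation | Power at -3.2, literal list | Baseline in | Baseline and KPS in |
|---|---|---|---|
| 0.2 | 0.808 | 0.812 | 0.807 |
| 0.35 | 0.776 | 0.793 | 0.788 |
| 0.5 | 0.723 | 0.760 | 0.755 |

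**Sensitivity, mid-range to strong.** The SAP cites week-7 completion of 82% and 57% in earlier studies. At 18% missing, KPS alone omitted gives -0.027 to -0.063 and the literal list with higher-pain dropout -0.068 to -0.144. At 43% missing the figures are -0.050 to -0.121 and -0.142 to -0.303. Scores rounded and bounded to 0-10, with KPS in tens from 60, give -0.040 to -0.092 and -0.098 to -0.204.

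**The case against.** The best case for the plan has four parts.

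- *Reading.* The bracketed list omits exactly the two scores that form the endpoint, so it may name only the additional visits, with baseline understood. That is plausible, and the larger figures (0.22 point, 4.9%, power 0.723) then fall away. The wording still does not settle it, and KPS stays out either way.
- *Size and evidence.* For KPS alone at mid-range, 2.6-2.7% cannot be told from 2.5%, and 0.04 is about 3% of the 1.2-point distance. No association used here is in the documents. The SAP reports that "approximately 82% (23/28) of subjects completed the 7 week follow up interval", so 28 - 23 = 5 had not, and their causes are not given; the 10 deaths among 11 early withdrawals cover 24 weeks. Entry requires KPS of at least 60 and life expectancy of at least 3 months, and Protocol 9.5 links KPS to prognosis, not to pain. All of this stands: whether bias exists in this trial, and how large, cannot be established from the documents.
- *Missingness pattern.* Telephone visits are allowed, and a subject who misses only week 8 may have later scores. With weeks 1, 4 and 12 observed, the bias falls to -0.01/-0.02/-0.05 (KPS omitted; weak/mid/strong) and -0.02/-0.04/-0.09 (literal list). Deaths before week 8 do not follow that pattern.
- *Other analyses.* Completer and last-observation-carried-forward analyses are planned and may show a divergence. They do not replace the designated test.

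**Conclusion.** The point holds as a cheap improvement, not as a flaw that invalidates the test. KPS is missing from the model on any reading, and baseline worst pain is not named. Under the assumed associations, omitting KPS alone overstates the reduction by 0.02 to 0.11 point (mid-range 0.04). Omitting baseline too gives a bias of 0.03 to 0.22 point (mid-range 0.10) in either direction, with 4.9% false success only in the strongest corner. With both variables in, the bias is at most 0.01. The power loss from leaving baseline out, 0 to 4 points, needs no link to dropout, only the literal reading and an assumed baseline to follow-up correlation. Confidence is medium, because every association is assumed.

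**What to change.** State in the SAP that the imputation model includes baseline BPI worst pain (item 3) and baseline KPS, together with worst pain at weeks 1, 4 and 8, age and gender. Keep the week 12 to 24 scores as auxiliary variables, to be dropped if the model does not converge. Settle this before outcomes are examined: the study is single-arm and unblinded, so a later change to the primary model would be post hoc.

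The cost is one sentence, with data already collected. The model becomes slightly larger with about 42 observed week-8 values. Adding KPS costs about 0.5 point of power (for example 0.793 to 0.788; Monte Carlo error 0.4 point). The change does not address data missing not at random, or whether a pain score should be imputed after death.
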